12.1 Patient Withdrawal/ Discontinuation/ Premature Study Termination

Once the patient has been enrolled in the study, he/she may withdraw his/her consent to participate in the study at any time without jeopardy or prejudice. Participation in this clinical investigation is entirely voluntary. Likewise, there may be a reason identified by the Investigator that deems the patient no longer suitable for the study. In either case, the Investigator should contact the study Sponsor, or its designee, to discuss the circumstances for discontinuation/withdrawal. Reasons for discontinuation or withdrawal may include, but are not limited to the following:

- The Investigator feels that the patient can no longer fully comply with the requirements of the study or if any of the study procedures would not be in the best interest of the patient.
- The patient is lost to follow-up. A patient will be considered "lost to follow-up" and terminated from the study when all of the following criteria have been met:
 - Failure to complete the remainder of the scheduled study visits without due cause; and
 - Documentation of three unsuccessful attempts to contact the patient via phone/email and/or registered mail.

PROTOCOL NUMBER: 2017-05

- The patient withdraws their consent for participation in the study.
- The patient incorrectly randomized in the study and treatment has not been initiated; or
- The Sponsor prematurely terminates the study. Circumstances under which the Sponsor can suspend or stop this trial include, but are not limited to, low study enrollment or new information regarding safety or efficacy.

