### 5. **DEFINITIONS**

### 5.1 Analysis Dates and Days

- Study start date is defined as the procedure date.
- Last information date is defined as the most recent date assessed with any available information concerning the patient (e.g., most recent date out of: baseline assessment, procedure, discharge, follow-up visits, laboratory tests, study termination, and adverse events). Last information date is used as censor date for survival analyses.
- Study day = Date Study start date

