Survival analysis techniques will be used to analyze the time-to-event variables. Patients without events will be censored at their last known event-free time point. If this event-free time point occurs after the analysis time point, the days to event variable will be set equal to the analysis time point so that the patient will be included in the analysis. For patients who did not have an event or early withdrawal and have not yet completed the analysis visit, they will be censored at the time of their last follow-up. Time to first event curves will be constructed using Kaplan-Meier estimates and all post discharge results will be summarized with Kaplan-Meier estimates of event rates. Hazard ratios, confidence interval for the hazard ratios, and p-values may also be presented from a Cox proportional hazards model.

Covariate analyses and variables of interest, as well as possible subgroup analyses of interest, may be performed to gain more clinical insight.

Descriptive statistics will be presented at each assessment, including change from baseline to subsequent time point for selected endpoints. Paired (i.e., patients with available data at both baseline and respective time point) and unpaired data will be presented separately.

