- Patients who are censored during the first year (includes patients who are lost to follow-up as well as patients who die due to non-cardiovascular causes) will be compared to other patients using available data up until the time at which the patient was censored. In other words, the number of heart failure hospitalizations up until the censoring time will be compared between the patient pair.
- Inclusion of hospitalizations is based on adjudication by the Clinical Events Committee (CEC).
- The index hospitalization for Edwards Cardioband System implant in patients randomized to Device group is not counted as heart failure related hospitalization. However, if the hospital stay is prolonged beyond 5 days because of a heart failure (HF) complication, it is counted as a HF-related hospitalization. This rule is also applies to surgical mitral annuloplasty or replacement that is performed during follow-up in patients randomized to Control.
- Hospitalizations beginning prior to the exact 1 year time point are counted for analysis of frequency of hospitalization.

THIS DOCUMENT CONTAINS CONFIDENTIAL AND PROPRIETARY INFORMATION OF EDWARDS LIFESCIENCES, LLC. IT MUST NOT BE REPRODUCED OR DISCLOSED TO THIRD PARTIES WITHOUT PRIOR WRITTEN PERMISSION OF EDWARDS LIFESCIENCES, LLC. (This template is required by DOC))

	2017-05 Sta	tistical Analysis Plan			1.0   7/16/20	19
$\mathbb{P}$	Revision Date: Febr	uary 28, 2019	Rev		For Use Only by Affiliates of Edwards Lifesciences	Page 13 of 18
Edwards	Title	Statistical Analysis Plan for ACTIVE 2017-05				

- The 6MWT and KCCQ data from the 1-year visit are used regardless of whether the visit is before or after the exact 1 year time point.
- If clinical follow-up of one or both patients is censored, the pairwise outcome assessment is performed on the basis of those events that occurred during the smaller of the two follow-up times. For example, if a Control patient experiences an event on a particular day, and the Device patient is censored on that day or a later day, then the pair favors Device.

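### SAP 5.1 and SAP 6.1 give conflicting censor dates; under 5.1 a lost patient's unobserved time can be counted as event-free

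*SAP*

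**What the plan says.** SAP 5.1 defines a last information date, by way of examples, as the latest of several dates. The list starts with baseline, procedure and discharge and continues: "follow-up visits, laboratory tests, study termination, and adverse events). Last information date is used as censor date for survival analyses".

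SAP 6.1 gives different rules for time-to-event variables: "Patients without events will be censored at their last known event-free time point". Patients with neither an event nor early withdrawal who have not yet had the analysis visit fall under a further rule: "they will be censored at the time of their last follow-up". Where the event-free date lies beyond the analysis time, "the days to event variable will be set equal to the analysis time point". Protocol 13.4.1 has the same text as 6.1. SAP 10 reports only one departure from the protocol, the enrolled population for roll-in patients, and does not mention censoring.

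Protocol 12.1 terminates a patient as lost when two conditions are both met. One is three documented failed contact attempts. The other is "Failure to complete the remainder of the scheduled study visits without due cause; and".

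For co-primary II, SAP 8.2 caps time-dependent events at one year from randomization and compares a pair over the shorter of their follow-up periods. For censored patients, "the number of heart failure hospitalizations up until the censoring time will be compared between the patient pair". It does not say which date ends follow-up for a lost patient, and it does not refer to 5.1.

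**The concern.** A lost patient's termination date, recorded after missed visits and failed calls, need not be a date on which anyone knew whether the patient was alive or had been hospitalized. If it sets the censor date, the gap since last contact is added to the risk set as event-free time. The 1-year cap limits the gap, but a patient carried to the cap looks like a full-year completer.

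The exposed analyses are:

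- **Directly:** the three secondary endpoints that are survival analyses, namely heart failure hospitalization (Andersen-Gill) and cardiovascular and all-cause death (log-rank), in SAP 8.4.
- **Possibly:** levels 1 and 2 of co-primary II. SAP 8.2 leaves the end of follow-up undefined, and 5.1 is the only itemised date derivation in the SAP. A patient carried to day 365 is neither censored nor missing at those levels, so neither the common-follow-up rule nor the rule that missing data are ties would protect the comparison.

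In both places the arm that loses more patients would look better. The trial is open-label and Controls learn that their scheduled procedure is cancelled (SAP 2.3), so unequal retention is plausible. SAP 6.2 sets out no sensitivity analysis that would reveal the effect, although Protocol 13.6 foresees multiple imputation and tipping-point analyses.

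**Working it through.** No figure in the plan depends on the censor date, so none can be reproduced for this point. As a check on the simulation, 300 fully evaluable patients gave 94.0% power for co-primary II. That agrees with the protocol synopsis (above 90%) but not with the 87% in Protocol 13.5 and SAP 8.11. With 375 patients, 20% lost and their partial data kept, power was 87.4%.

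**Inputs from the plan**
- 375 patients at 2:1, so 250 Device and 125 Control; two-sided alpha 0.05; dropout up to 20%; 1-year mortality 20% in both arms; 6MWT and KCCQ responders 50% Device and 10% Control (SAP 8.11).
- Heart failure counts (SAP 8.11), taking five or more as five: Control mean 0.10×1 + 0.10×2 + 0.10×3 + 0.05×4 + 0.05×5 = 1.05; Device mean 0.10×1 + 0.05×2 + 0.05×3 + 0.05×4 + 0.05×5 = 0.80.
- Year-1 visits at 30 days, 180 days and 1 year (Protocol 9).

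**Assumptions not in the plan:** constant death hazard; loss times and heart failure events uniform over the year; components independent; loss unrelated to prognosis; no deaths recovered from registries; the split of loss by arm.

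**Step 1: longest unobserved interval under the cap.** Last seen at day 180: 365 − 180 = 185 days. Last seen at day 30: 365 − 30 = 335 days.

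**Step 2: 1-year mortality if all lost patients are carried to day 365.** The hazard is λ = −ln(0.80) = 0.22314 per year. The chance of dying before a uniform loss time is q = 1 − (1 − e^(−λ))/λ = 1 − 0.20/0.22314 = 0.1037. With a fraction ℓ lost, the estimate is (1 − ℓ)×0.20 + ℓ×q.
- ℓ = 20%: 0.1600 + 0.0207 = 18.1%.
- ℓ = 5%, 10%, 30%: 19.5%, 19.0%, 17.1%.
- ℓ = 20%, all last seen at day 180: q = 1 − e^(−λ×180/365) = 0.1042, giving 18.1%. All last seen at day 30: q = 0.0182, giving 16.4%.

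**Step 3: simulation.** The Finkelstein-Schoenfeld statistic L = T/√V of SAP 8.2 was computed twice on each simulated trial: with lost patients censored at last contact, and with them counted as event-free to a later date. There were 5,004 trials per row, or 1,504 for the 90-day lag. Monte Carlo standard errors are about 0.3 to 0.9 points. Under the null, both arms have the Control assumptions.

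| Loss, Device/Control | Quantity | Last contact | Later date |
|---|---|---|---|
| 20%/20%, to day 365 | 1-year mortality | 20.0% | 18.1% |
| | HF per patient-year, Control | 1.05 | 0.94 |
| | HF per patient-year, Device | 0.80 | 0.72 |
| | Power, co-primary II | 87.4% | 83.6% |
| | Type I error | 5.0% | 4.7% |
| 20%/20%, 90-day lag | Power, co-primary II | 86.8% | 85.7% |
| | 1-year mortality | about 20% | about 19.2% |
| 10%/30%, to day 365 | Power, co-primary II | 85.7% | 59.4% |
| | Type I error | 4.8% | 11.2% |
| 30%/10%, to day 365 | Type I error | 4.9% | 10.1% |

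The heart failure rates fall by 1 − 0.94/1.05 = 10% (Control) and 1 − 0.72/0.80 = 10% (Device).

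With 10%/30% loss, only 0.3 of the 11.2 points of false results favour Device; the rest favour Control. With 30%/10% loss, 9.6 of the 10.1 points favour Device. Overall loss is 25 + 37.5 = 62.5 of 375 (16.7%) in the first case and 75 + 12.5 = 87.5 of 375 (23.3%) in the second. The second exceeds the plan's 20%.

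**The case against.** A reader might infer that the SAP simply censors at termination, that lost patients are therefore carried event-free long after last contact, and that co-primary II is biased. The documents do not support that, for these reasons:

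- The sound rule is also written down, in SAP 6.1 and Protocol 13.4.1.
- The list in 5.1 only gives examples of dates with available information about the patient. An administrative closure without contact arguably is not such a date.
- 5.1 is limited to survival analyses, and SAP 8.2 has its own rules and never invokes it.
- No document says which date is recorded as termination for a lost patient. Visits run to 5 years, so on a literal reading of Protocol 12.1 a patient lost at day 180 would have no termination date by the 1-year analysis. On a looser reading, termination could fall well before day 365.
- Protocol 12.2 asks for an exit visit before termination, which would make that date a real contact. Protocol 12.3 asks for a death-registry search when possible.
- The larger figures need every lost patient carried to day 365 and a threefold difference in loss between arms, which nothing in the plan supports.

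All of this limits the claim, but the conflict remains. Study termination is named in the list, and a programmer following 5.1 would probably code it. The registry search covers deaths, not heart failure hospitalizations. SAP 10 does not disclose that 5.1 departs from the protocol's rule.

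**Conclusion.** The SAP contains two censoring rules that can give one lost patient two different dates, and the rule in 5.1 can count unobserved time as event-free. The three secondary survival endpoints fall directly under it. Co-primary II can be affected at levels 1 and 2 because 8.2 leaves the end of follow-up open, but bias there is a possibility, not a demonstrated result.

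With equal loss the harm is modest. Mortality and heart failure rates are understated, and co-primary II loses about 4 points of power in the worst case or about 1 point with a 90-day lag, with no type I error inflation. A biased comparison requires unequal loss. It then favours the arm that loses more patients, so the direction cannot be stated in advance. The type I error of about 11% at 10% Device / 30% Control loss is a worst-case illustration on an assumed split. All sizes rest on the assumptions listed with the calculation, including loss unrelated to prognosis.

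The conflict should be settled before unblinding, because choosing between the two rules afterwards could change a result.

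**What to change.** In SAP 5.1, let the study-termination date censor a patient only when it is itself a contact, such as an exit visit or a consent-withdrawal conversation. Otherwise censor each endpoint at the last date on which its own status was ascertained:

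- **Death:** last confirmed vital status. Use the registry search date only where the search was done for survivors and deaths alike. Counting registry deaths while censoring registry survivors at last contact would bias mortality upward.
- **Heart failure hospitalization:** last contact at which hospitalizations were ascertained.

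A single date for all endpoints would discard survival time confirmed by the registry search. Keep the existing 1-year cap, align the wording of 5.1 with 6.1, and cite these dates in SAP 8.2 as the end of follow-up for the pairwise comparisons: the death date rule at level 1 and the hospitalization rule at level 2.

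The cost is a short SAP edit, one changed derivation and slightly shorter event-free follow-up. No new data are needed.

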### 5.2 Visit Windows

Assessments are considered by their nominal visit name (e.g., "30 days" and "1 year") regardless of whether the actual visit date is within the protocol defined visit window.

- 30 Days: Day 23 Day 37
- 6 Months: Day 166 Day 194
- 1 Year: Day 320 Day 410
- 2 Years: Day 670 Day 790
- 3 Years: Day 1035 Day 155
- 4 Years: Day 1400 Day 1520
- 5 Years: Day 1765 Day 1885

### 6. DATA AND ANALYSIS CONVENTIONS

### 6.1 General Conventions

All data collected will be summarized overall and by treatment groups.

For continuous variables (e.g., age, percent diameter stenosis, and lesion length), results within treatment group will be summarized with the numbers of observations, means, medians, standard deviations, minimums, maximums, and 95% confidence intervals per table mockups. Differences between the treatment groups, where specified, will be summarized with the differences of the two means and 95% confidence intervals for the difference between the means, and p-values based on a t-test. The distributions within each group will be tested for normality using the Shapiro-Wilks test and if normality cannot be assumed then a Wilcoxon rank-sum test and 95% confidence interval of the median will be presented. The confidence interval for the difference of two means will be calculated under the assumption of unequal variances.

For categorical variables (e.g., gender, in-hospital event rates, and angina status), results within treatment group will be summarized with patient counts and percentages. Differences between the two treatment groups, where specified, will be

THIS DOCUMENT CONTAINS CONFIDENTIAL AND PROPRIETARY INFORMATION OF EDWARDS LIFESCIENCES, LLC. IT MUST NOT BE REPRODUCED OR DISCLOSED TO THIRD PARTIES WITHOUT PRIOR WRITTEN PERMISSION OF EDWARDS LIFESCIENCES, LLC. (This template is required by DOC ))

	2017-05 Sta	tistical Analysis Plan			1.0   7/16/20	19
	Revision Date: Febr	uary 28, 2019	Rev		For Use Only by Affiliates of Edwards Lifesciences	Page 10 of 18
Edwards	Title	Statistical Analysis Plan	for	ACTIVE	2017-05	

summarized with the difference in percentages, the asymptotic 95% confidence interval for the difference of two percentages, and a p-value based on a chi squared test. If 20% or more of the expected cell frequencies are less than 5, a Fisher's exact test will be used to test for differences in proportions.

For the determination of event rates in-hospital, the number of all patients in the patient population will be used as the denominator. For variables ascertained at follow-up, the denominator will be only those patients who had follow-up performed at that time point. Unless otherwise noted, patients with missing data are excluded from the denominator.

Survival analysis techniques will be used to analyze the time-to-event variables. Patients without events will be censored at their last known event-free time point. If this event-free time point occurs after the analysis time point, the days to event variable will be set equal to the analysis time point so that the patient will be included in the analysis. For patients who did not have an event or early withdrawal and have not yet completed the analysis visit, they will be censored at the time of their last follow-up. Time to first event curves will be constructed using Kaplan-Meier estimates and all post discharge results will be summarized with Kaplan-Meier estimates of event rates. Hazard ratios, confidence interval for the hazard ratios, and p-values may also be presented from a Cox proportional hazards model.

Covariate analyses and variables of interest, as well as possible subgroup analyses of interest, may be performed to gain more clinical insight.

Descriptive statistics will be presented at each assessment, including change from baseline to subsequent time point for selected endpoints. Paired (i.e., patients with available data at both baseline and respective time point) and unpaired data will be presented separately.

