13.4 Statistical Methods

13.4.1 General Approach

All data collected will be summarized overall and by treatment groups.

For continuous variables (e.g., age, percent diameter stenosis, and lesion length), results within treatment group will be summarized with the numbers of observations, means, medians, standard deviations, 25th and 75th percentiles, minimums, and maximums per the table mockups. Differences between the treatment groups, where specified, will be summarized with the differences of the two means, 95% confidence intervals for

the difference between the means, and p-values based on a t-test. The distributions within each group will be tested for normality using the Shapiro-Wilks test and if normality cannot be assumed then a Wilcoxon rank-sum test and 95% confidence interval of the median will be presented. The confidence interval for the difference of two means will be calculated under the assumption of unequal variances.

For categorical variables such as gender, in-hospital event rates, and angina status, results within treatment group will be summarized with patient counts and percentages. Differences between the two treatment groups, where specified, will be summarized with the difference in percentages, the asymptotic 95% confidence interval for the difference of two percentages, and a p-value based on a chi-squared test. If 20% or more of the expected cell frequencies are less than 5, a Fisher's exact test will be used to test for differences in proportions.

For the determination of event rates in-hospital, the number of all patients in the patient population will be used as the denominator. For variables ascertained at followup, the denominator will be only those patients who had follow-up performed at that time point. Unless otherwise noted, patients with missing data are excluded from the denominator.

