#### 2.3 Randomization and Blinding

Randomization is ideally performed within seven days prior to the scheduled procedure, but no more than 14 days prior. If a patient is randomized to Control, the scheduled interventional case is cancelled and the patient is notified that they have been enrolled in the Control/medical therapy arm of the trial and will not need to undergo an interventional procedure. The process of randomizing after a case is scheduled has been implemented to ensure that the time frame between randomization and actual treatment is minimized. Eligible patients will be randomly assigned in a 2:1 ratio to either Device group or Control group, respectively.

Randomization schedule will be generated using the Balance module in Medidata RAVE, the Electronic Data Capture System for the study. Randomization will be stratified by (a) site and (b) baseline ischemic vs non-ischemic disease. This randomization schedule will be masked to patients, site personnel, study team, and sponsor as defined in the Randomization and Blinding Plan. Only the unblinded statistician and designates will be privy to the masked randomization scheme.

All analyses of data by the study statistician/programmer will be conducted blinded to treatment assignment (similar to the conduct of blinded clinical study to the extent possible), until the time of database lock for the primary endpoint analysis. Analyses of unblinded data such as DSMB analysis will be performed by a separate non-study or independent statistician/SAS programmer.

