### 4.3 Modified Intent-to-Treat Population (Efficacy Analysis)

The modified intent-to-treat population (mITT) will consist of all patients randomized to the Control Group and all patients randomized to the Device group that have had the Edwards Cardioband System implanted. The mITT population represents the primary analysis population for this study. The randomization will continue until 375 mITT patients are enrolled.

THIS DOCUMENT CONTAINS CONFIDENTIAL AND PROPRIETARY INFORMATION OF EDWARDS LIFESCIENCES, LLC. IT MUST NOT BE REPRODUCED OR DISCLOSED TO THIRD PARTIES WITHOUT PRIOR WRITTEN PERMISSION OF EDWARDS LIFESCIENCES, LLC. (This template is required by DOC.))

E	Revision Date: February 28, 2019		Rev		For Use Only by Affiliates of Edwards Lifesciences	Page 9 of 18
Edwards	Title	Statistical Analysis Plan	for	ACTIVE	2017-05	

A separate summary of the safety on all screen failure patients shall be provided as part of the study final report.

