### 8.8 Long Term Safety Outcomes (5 Years)

Descriptive statistics for long term safety outcomes will be compared between Device and Control groups.

THIS DOCUMENT CONTAINS CONFIDENTIAL AND PROPRIETARY INFORMATION OF EDWARDS LIFESCIENCES, LLC. IT MUST NOT BE REPRODUCED OR DISCLOSED TO THIRD PARTIES WITHOUT PRIOR WRITTEN PERMISSION OF EDWARDS LIFESCIENCES, LLC. (This template is required by DOC.))

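### For sparse events SAP 6.1 moves the p-value to Fisher's exact test but leaves the interval asymptotic with no formula named; if that means Wald, interval and p-value can disagree (minor)

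*SAP*

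**What the plan says.** SAP 6.1 (General Conventions) summarises a between-arm difference in a categorical variable, where a comparison is specified, with "the asymptotic 95% confidence interval for the difference of two percentages, and a p-value based on a chi squared test". The next sentence deals with sparse tables: "If 20% or more of the expected cell frequencies are less than 5, a Fisher's exact test will be used". It replaces the test and says nothing about the interval. Protocol 13.4.1 (General Approach) follows the same scheme: "the asymptotic 95% confidence interval for the difference of two percentages, and a p-value based on a chi-squared test", then a Fisher switch for the test alone. Neither document gives a formula for the asymptotic interval.

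The arm sizes follow from SAP 4.3 ("The randomization will continue until 375 mITT patients are enrolled") and SAP 2.3 ("Eligible patients will be randomly assigned in a 2:1 ratio to either Device group or Control group, respectively").

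For means, SAP 6.1 is specific about the interval ("The confidence interval for the difference of two means will be calculated under the assumption of unequal variances") but says only that the p-value comes from a t-test.

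**The concern.** The Fisher rule concedes that large-sample inference is unreliable in sparse tables, yet in those same tables the plan keeps a large-sample interval. On the usual Wald reading, an arm with no events contributes nothing to the standard error, so the interval is too short. With no events in either arm it has zero width.

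A reader of a safety table could then see an interval that excludes zero beside a p-value that is clearly non-significant. Because Control is the smaller arm, it is the more likely to show zero events, so the error tends to suggest that Device is worse.

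**Working it through.** **Inputs.** N = 375 (SAP 4.3) at 2:1 (SAP 2.3), taken as 250 Device and 125 Control. Range checks: 200 vs 100 (300 evaluable) and 150 vs 75 (60% of 375 = 225), both from SAP 8.11. Event counts and event rates below are assumptions; the documents give none for these outcomes.

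**The plan's own figure.** The documents state no figure on this point. As a check of the arm sizes, take co-primary 1 at 10% vs 70% with 75 and 150 patients. The pooled proportion is (7.5 + 105)/225 = 0.5, with null SE √(0.25 × (1/75 + 1/150)) = 0.0707. The unpooled SE is √(0.09/75 + 0.21/150) = 0.0510. Then (0.60 − 1.96 × 0.0707)/0.0510 ≈ 9.05, so power exceeds 99%, as stated. The smallest expected cell is 112.5/3 = 37.5, so this endpoint is not sparse.

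**When Fisher applies.** A 2×2 table has four cells, so one cell below 5 is 25% and meets the rule. With E events in total, the Control expected count is E × 125/375 = E/3. This is below 5 when E < 15.

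**4 vs 0 at 250 vs 125.** Expected event counts are 2.67 and 1.33, so Fisher applies.
- Wald: d ± 1.96 × √(p₁(1−p₁)/n₁ + p₂(1−p₂)/n₂), with d = 1.6% and SE = √(0.016 × 0.984/250 + 0) = 0.794%. The interval is 0.045% to 3.155%.
- Fisher, two-sided: the tables no more probable than the observed one are 4, 1 and 0 events in Device, with probabilities 0.196 + 0.098 + 0.012 = 0.306.
- The uncorrected chi-square p is 0.155, so Fisher's conservatism is not the sole cause.
- At 200 vs 100 the interval is 0.06% to 3.94% with p = 0.305. At 150 vs 75 it is 0.09% to 5.25% with p = 0.304.

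**All conflicts below 15 events.** Enumerating every table at 250 vs 125, Wald excludes zero with Fisher p > 0.05 in nine, all in the direction Device worse:

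| Device vs Control events | Wald 95% CI (%) | Fisher p | Newcombe 95% CI (%) |
|---|---|---|---|
| 4 vs 0 | 0.04 to 3.16 | 0.31 | −1.54 to 4.04 |
| 5 vs 0 | 0.26 to 3.74 | 0.17 | −1.19 to 4.60 |
| 6 vs 0 | 0.50 to 4.30 | 0.18 | −0.85 to 5.14 |
| 7 vs 0 | 0.76 to 4.85 | 0.10 | −0.51 to 5.67 |
| 8 vs 0 | 1.02 to 5.38 | 0.056 | −0.17 to 6.19 |
| 9 vs 1 | 0.01 to 5.59 | 0.17 | −1.17 to 5.97 |
| 10 vs 1 | 0.31 to 6.09 | 0.11 | −0.82 to 6.47 |
| 11 vs 1 | 0.62 to 6.58 | 0.068 | −0.48 to 6.97 |
| 12 vs 1 | 0.92 to 7.08 | 0.068 | −0.13 to 7.46 |

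For 4 vs 0, Miettinen-Nurminen gives about −1.4% to 4.05%. At 0 vs 0 the Wald interval is 0 to 0.

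**Coverage.** Sum Bin(x; 250, p) × Bin(y; 125, p) over all tables whose interval contains zero, with the same true rate p in both arms:

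| Assumed rate | Wald coverage | Wholly above 0 (Device worse) | Wholly below 0 | Newcombe coverage |
|---|---|---|---|---|
| 0.5% | 97.9% | 2.0% | 0.1% | 99.1% |
| 1% | 92.5% | 6.9% | 0.5% | 97.9% |
| 1.5% | 90.9% | 8.2% | 0.9% | 97.1% |
| 2% | 91.6% | 7.3% | 1.1% | 96.6% |
| 3% | 93.0% | 5.7% | 1.3% | 96.2% |
| 5% | 94.3% | 4.2% | 1.5% | 95.7% |

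The nominal tail on each side is 2.5%. A Wald interval excluding zero beside a non-significant Fisher test occurs in 2.0%, 6.9%, 8.0%, 6.7% and 3.9% of trials at rates of 0.5%, 1%, 1.5%, 2% and 3%.

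**The case against.** The strongest reply concerns reach, and most of it stands. SAP 6.1 gives a difference, interval and p-value only where a comparison is specified. SAP 8.8 promises only this: "Descriptive statistics for long term safety outcomes will be compared between Device and Control groups". SAP 9.2 treats adverse events descriptively. SAP 6.1 also sends post-discharge results to Kaplan-Meier estimates, which would cover most stroke, TIA, vascular and renal events through one year. The primary and secondary 30-day safety endpoints (SAP 3.4 and 3.5) are Device-only, so they have no between-arm difference. SAP 8.5 does pair between-arm comparisons with confidence intervals, but for success and responder outcomes and with no p-value.

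The second reply also stands in part: the plan says asymptotic, not Wald. A score interval is itself a large-sample method and would fit the wording, and even a continuity-corrected Wald interval includes zero at 4 vs 0 (−0.56% to 3.76%). So a reader should not infer that the SAP prescribes Wald. That leaves a choice open that decides whether the conflict occurs, which is a reason to name the formula.

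Third, the size depends on the assumed rate. Coverage of 90.9% is the lowest value in the table and not typical, and at 4 vs 0 the lower limit clears zero by only 0.045 percentage points.

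What remains is that the plan states one rule for the interval of a difference in percentages, and that rule has no provision for the sparse case it recognises for the test. The Kaplan-Meier paragraph names no interval for a between-arm difference either.

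**Conclusion.** The point holds as a minor one. Both documents switch the test but not the interval in sparse tables. On the usual Wald reading this produces nine conflicting tables below 15 events at 250 vs 125, a zero-width interval at 0 vs 0, and coverage between 90.9% and 97.9% over assumed event rates of 0.5% to 5%, with errors mostly towards Device worse.

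It rests on three assumptions: that asymptotic means unpooled Wald, that the arms are close to 250 and 125, and that rare events (in-hospital events, or stroke, TIA, vascular and renal outcomes) are compared as simple proportions and not as Kaplan-Meier rates.

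A reader might infer that the trial's safety conclusion or its alpha-controlled tests are at risk. The documents do not support that. The formal safety endpoints have no Control comparison, co-primary 1 is far from sparse at the planning rates, and the gated binary endpoints are decided by their tests and not by this interval. The means wording is an unspecified detail: no pooled t-test is stated, and the documents give no variances from which to size an effect.

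**What to change.** In SAP 6.1 and Protocol 13.4.1, specify a score interval (Newcombe or Miettinen-Nurminen) for between-arm differences in percentages, at least whenever the Fisher rule applies; using it throughout is simpler. In all nine conflicting tables above, the Newcombe interval includes zero, in line with Fisher.

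Agreement is not guaranteed in every table. At 3 vs 6 events the Wilson limits are 0.41% to 3.47% and 2.22% to 10.08%. The Newcombe upper limit is −3.6% + √((3.47 − 1.20)² + (4.80 − 2.22)²)% ≈ −0.16%, against Fisher p = 0.065. The SAP could add one sentence saying that the two methods may differ at the margin.

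Optionally, state that the t-test p-value uses the same unequal-variance (Welch) form as the interval for means.

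The cost is a wording change and a standard software option, with no new data. Intervals for rare events become somewhat wider, and Newcombe is mildly conservative at very low rates (99.1% coverage at 0.5%).
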